15.6 Analysis of Exploratory Endpoints

Mutational load analysis and tumor cell population clonality:

Whole exome sequencing will be performed to evaluate the genomic frequency and pattern of mutations as well as the clonality of the tumor cell population, using tumor tissue resected prior to nivolumab treatment (initial diagnosis and post-alkylating agent whenever tissue is available). Germline DNA from peripheral blood mononuclear cells will be used as controls for each participant. None of the somatic or germline whole exome sequencing results will be returned to participants or treating physicians.

We will correlate ORR with mutational burden using chi-square or Fisher exact test as appropriate for this exploratory analyses.

If subsequent surgeries for tumor recurrence are done following treatment with nivolumab, the clonal evolution of these tumors will be studied through computational modeling, as developed by the team of our collaborator, [name], in the Department of Systems Biology at Columbia University Medical Center

Imaging Biomarkers

2HG will be measured non-invasively through magnetic resonance spectroscopy (MRS) added to standard of care MRI scans at baseline and every 8 week assessments. Analysis will be descriptive as this is an exploratory biomarker.

Spatial Profiling of PD-1/PD-L1 Interaction

Slides from tumor samples will be fluorescently stained with multiple immunomarkers using immunohistochemistry. Novel algorithms, developed by our collaborator [name] at Vanderbilt University, are used to objectively quantify biomarker positive cells and their co-localization and flow cytometry is used to identify these cells. A PD-1/PD-L1 interaction score is generated and this will be correlated with response to treatment.

Neurologic Assessment in Neuro-Oncology

Descriptive analyses of NANO scale and correlation with MRI will be performed.

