2.3 Exploratory Objectives

- To correlate response rate to nivolumab with mutational load analyses and specific tumor mutations
- To study clonal evolution of the tumor cell populations in IDH mutated gliomas undergoing therapy whenever tumor tissue is available
- To evaluate the longitudinal changes in the IDH mutant metabolite product 2-hydroxyglutarate (2HG) using magnetic resonance spectroscopy
- To evaluate spatial profiling of PD-1/PD-L1 interaction in IDH mutated gliomas and response to nivolumab

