In comparison to other cancer types with a robust response to immunotherapy such as melanoma and non-small cell lung cancer associated with smoking, untreated gliomas have a relatively small mutational burden. A recent study by [name] at Columbia University involved whole exome and transcriptome analyses of untreated and recurrent tumors from 114 subjects with glioblastomas. Among the 114 untreated tumors, the average number of somatic mutations was 60. In comparison, the average number of mutations in subjects with non-small cell lung cancer who achieved durable clinical benefit from PD-1 inhibitors was 302 vs. 148 in subjects who did not achieve a durable benefit. One exception to this is in glioblastomas arising in children with a rare germline cancer syndrome, biallelic mismatch repair deficiency (bMMRD). These tumors tend to have a high mutational burden (mean of 17,740 mutations compared to <100 in untreated glioblastomas and other gliomas). Two subjects with glioblastoma associated with bMMRD were treated with anti-PD1 inhibitor with dramatic clinical and radiographic responses.²⁰

It has long been reported that the use of alkylating agents in gliomas is associated with a risk of higher-grade transformation and development of a hypermutated genotype with MSH6 mutations; however, the incidence in unselected subjects is very rare.^{10,11} A recent study

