investigated mutations induced by temozolomide by comparing pre and post-temozolomide glioblastoma specimens.²² In IDH mutant low grade gliomas that progressed after temozolomide, six out of ten subjects recurred with hypermutated tumors.²³ Consistent with results from IDH mutant low grade gliomas that transformed to high-grade gliomas following temozolomide, an IDH1 mutated secondary glioblastoma subject showed a dramatically increased number of somatic mutations compared with the matched temozolomide naïve tumor (4848 vs. 119). This case also had mutations in mismatch repair genes PMS1 and MSH5. In contrast, none of the 20 subjects with IDH1 wild type glioblastoma showed any increase in the total or temozolomide-associated mutations in recurrent tumors when compared to initial tumors.²² In [name] study, almost all subjects received an alkylating agent prior to progression with temozolomide being the most common. Of 21 IDH mutant tumors, 9 (43%) developed a hypermutated recurrent tumor (>500 mutated genes/tumor) at recurrence. In comparison, only 8 of 93 (9%) IDH wildtype tumors developed a hypermutated tumor at recurrence (Fisher's exact test P=0.0005).

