15.2 Size/Accrual Rate

Based on prior historical data showing an overall response rate (ORR) of 9% in recurrent high-grade gliomas (grade III and IV)³⁹, and 0% on the IDH inhibitor trial (AG-221)³ we set the null hypothesis of an ORR = 10% and the alternative hypothesis of an ORR = 30%. With one-sided $\alpha=0.05$ and $\beta=0.10$, a sample size of 33 evaluable participants will be needed to assess the preliminary efficacy of this regimen. We expect to accrue a total of 37 participants across all sites to account for a 10% of participants who may be deemed unevaluable for response.

We expect an accrual rate of 3 participants per month.

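### Section 15.6 tests mutational burden against response only with categorical tests, at a cut it never fixes; a pre-specified analysis of log mutation count costs no extra data and guards against lost power and a data-driven cut

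*Combined protocol and SAP*

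**What the plan says.** Section 2.3 lists as its first exploratory objective: "To correlate response rate to nivolumab with mutational load analyses and specific tumor mutations". Section 15.6 gives the source of the burden measure, "Whole exome sequencing will be performed to evaluate the genomic frequency and pattern of mutations as well as the clonality of the tumor cell population", and then the test: "We will correlate ORR with mutational burden using chi-square or Fisher exact test as appropriate for this exploratory analyses". It states no cut, number of categories, significance level, effect size or power for this analysis, and no rank or continuous alternative.

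The one threshold in the documents is in Section 3, about a separate cohort: "Of 21 IDH mutant tumors, 9 (43%) developed a hypermutated recurrent tumor (>500 mutated genes/tumor) at recurrence". Neither Section 5.5 nor Section 15.6 carries it forward.

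**The concern.** A chi-square or Fisher test cannot use a mutation count until someone cuts it into groups. That has two consequences.

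- **Lost information.** Tumors on the same side of the cut are treated as alike. If the chance of response rises steadily with burden, this costs power, and only about 10 responders are expected (33 x 0.30 = 9.9).
- **An open cut.** Nothing in 15.6 stops the cut from being chosen once response is known, which would inflate the false-positive rate.

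The idea that mutational load makes these gliomas sensitive to PD-1 blockade is the trial's scientific rationale, and this sentence is the only planned test of burden against response.

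**Working it through.** **1. The plan's own figures.** Section 15.2 says "we set the null hypothesis of an ORR = 10% and the alternative hypothesis of an ORR = 30" percent, with one-sided alpha 0.05, power 0.90 and 33 evaluable participants. By the exact binomial, 33 is the smallest n that works: declaring success at 7 or more responses gives P(X >= 7 | 0.10) = 0.0417 and P(X >= 7 | 0.30) = 0.9056. Accrual is 33 / 0.90 = 36.7, rounded up to 37. Section 3's comparison of hypermutation, 9/21 against 8/93, gives a Fisher p of 0.00045, matching the stated 0.0005. No power is stated for the burden analysis, so there is nothing to reproduce there.

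**2. Which planned test would apply.** With 43% hypermutated and a 30% response rate, the expected number of hypermutated responders is 33 x 0.43 x 0.30 = 4.26. This is below 5, so the usual reading of the plan's rule (Fisher if any expected count is below 5, otherwise chi-square) leads to Fisher. In simulated two-cluster trials the rule chose Fisher 71 to 76% of the time.

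**3. Power, planned rule against log count.** From the documents: n = 33, response rate 30%, 43% above the cut in the two-cluster case, cut at 500. Assumed: two-sided 5%; usable exome data for all 33; log-normal counts, either two clusters (medians 80 and 2500, log-SD 0.6 and 0.8) or one (median 300, log-SD 1.5). Rows within a shape differ in the assumed strength of the relation. There were 3,000 to 4,000 trials per scenario.

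| Assumed relation | Planned rule | Log count | Difference (points) |
|---|---|---|---|
| Two clusters, graded | 36% | 47-48% | +11 to +12 |
| | 66% | 78-79% | +12 to +13 |
| | 85% | 93% | +8 |
| One cluster, graded | 19% | 31% | +12 |
| | 36% | 54-58% | +18 to +22 |
| | 60% | 82-85% | +22 to +25 |
| Pure step at 500 | 51% | 51-52% | 0 to +1 |
| | 75% | 73-74% | -2 to -1 |

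The gap narrows as power nears its ceiling: in a steep two-cluster graded case, Fisher alone reached 94% and log count 98%.

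**4. How much is due to the cut.** Two-cluster graded case, same 500 cut, 2,000 runs:

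| Response rate above / below 500 | Fisher | Uncorrected chi-square | t-test on log count |
|---|---|---|---|
| 46% / 18% | 35% | 44% | 49% |
| 53% / 13% | 63% | 71% | 77% |

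Categorising costs 49 - 44 = 5 and 77 - 71 = 6 points. Using Fisher instead of chi-square costs 44 - 35 = 9 and 71 - 63 = 8. Fisher's actual size under no association was 3.0%, against 5.0% for the log-count test.

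**5. A cut chosen afterwards.** With no association, n = 33 and a 30% response rate, taking the smallest Fisher p over all cuts that leave at least 8 per side rejects about 17% of the time at a nominal 5% (20% with at least 5 per side). This needs no assumption about effect size or the shape of the counts.

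**6. Which continuous test.** In the two scenarios of step 4, logistic regression had 45% and 72% power with a Wald test but 50% and 78% with a likelihood-ratio test, so the choice must be written down. Mann-Whitney is not a good substitute. In a separate two-cluster simulation cut at 500 (clusters centred at 70 and 2000), it was 2 to 5 points below chi-square in graded cases, and 8 to 9 below Fisher in a step case.

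**The case against.** The strongest reply is that the cut suits the biology. Section 3 argues for a hypermutated state in glioma: 43% of IDH mutant recurrences passed a threshold, and one case "showed a dramatically increased number of somatic mutations compared with the matched temozolomide naïve tumor (4848 vs. 119"). If response steps up at that state, a two-group test is the natural one. In step scenarios (response 49/16, 54/13 and 60/8% above/below the cut) uncorrected chi-square had 53, 74 and 93% power against 47, 67 and 88% for the t-test on log count: 6, 7 and 5 points better. This stands. It is why the size of the concern is a range that starts at about zero.

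A reader might infer that the protocol's own rationale is graded, because Section 3 gives average counts in lung cancer patients "who achieved durable clinical benefit from PD-1 inhibitors was 302 vs. 148 in subjects who did not achieve a durable benefit". The documents do not support that. Those figures are group averages from another disease, used to show how few mutations untreated gliomas carry. They also count mutations, whereas the 500 threshold counts mutated genes, so they cannot be scored against it.

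It is also fair that the analysis is labelled exploratory, that the same objective covers specific mutations (for which a categorical test is right), and that a post hoc search for a cut is left open but not planned. None of this supplies the missing cut or a reason to omit a continuous analysis.

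**Conclusion.** The concern holds in limited form. Section 15.6 commits an exome mutation count to categorical tests without fixing a cut, and the only candidate threshold sits in the background.

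A reader might infer a definite power loss, all of it caused by categorising. The documents support neither: they give no burden distribution, effect size or significance level for this analysis. At n = 33 and a 30% response rate, the loss against the plan's rule with a 500 cut is roughly 8 to 25 points if the relation is graded, less where power is already near its ceiling, and about none if it is a step. Part of any loss is Fisher's conservatism. The error rate of about 17% applies only if the cut is chosen after response is known. Fewer usable tissue samples would lower the power of every test.

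The primary conclusion is unaffected, so the priority is low. The change is still worth making because it is cheap.

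**What to change.** Before response is linked to the sequencing results, replace the burden sentence in Section 15.6 with wording to this effect:

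- The main exploratory burden analysis relates response (CR or PR against neither) to log mutation count as a continuous variable. It uses logistic regression with a likelihood-ratio test, or a permutation test of mean log count between responders and non-responders. Name one of the two. Report the odds ratio per doubling with its 95% confidence interval.
- A supportive 2x2 table shows response by hypermutation status with Fisher's exact test, at the single pre-specified cut of more than 500 mutated genes per tumor.
- Fisher's exact test is kept for specific mutations, which are binary.

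State what is counted in each analysis, since Section 3 uses both mutations and mutated genes.

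The cost is a few lines of text, with no added patients, samples or procedures. An odds ratio per doubling is less familiar to clinicians than a 2x2 table, which is why the table stays. If the effect is a pure step, the continuous test gains nothing over the planned rule and is about 5 to 7 points below uncorrected chi-square.

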15.7 Reporting and Exclusions

Evaluation of toxicity

All participants will be evaluable for toxicity from the time of their first treatment with the study drug.

Evaluation of response

All participants included in the study must be assessed for response to treatment, even if there are major protocol treatment deviations or if they are ineligible. Each participant will be assigned one of the following categories: 1) complete response, 2) partial response, 3) stable disease, 4) progressive disease, 5) early death from malignant disease, 6) early death from toxicity, 7) early death because of other cause, or 9) unknown (not assessable, insufficient data). [Note: By arbitrary convention, category 9 usually designates the “unknown” status of any type of data in a clinical database.]

All of the participants who met the eligibility criteria (with the possible exception of those who received no study medication) should be included in the main analysis of the response rate. Participants in response categories 4-9 should be considered to have a treatment failure (disease progression). Thus, an incorrect treatment schedule or drug administration does not result in exclusion from the analysis of the response rate. Precise definitions for categories 4-9 will be protocol specific.

All conclusions should be based on all eligible participants. Subanalyses may then be performed on the basis of a subset of participants, excluding those for whom major protocol deviations have been identified (e.g., early death due to other reasons, early discontinuation of treatment, major protocol violations, etc.). However, these subanalyses may not serve as the basis for drawing conclusions concerning treatment efficacy, and the reasons for excluding participants from the analysis should be clearly reported. The 95% confidence intervals should also be provided.

16 PROTECTION OF HUMAN SUBJECTS

This study is to be conducted in accordance with applicable government regulations and Institutional research policies and procedures.

Columbia University Medical Center
Herbert Irving Comprehensive Cancer Center
Version Date: January 30, 2024

This protocol and any amendments will be submitted to a properly constituted Institutional Review Board (IRB), in agreement with local legal prescriptions, for formal approval of the study conduct. The decision of the IRB concerning the conduct of the study will be made in writing to the investigator and a copy of this decision will be obtained before commencement of this study.

All subjects for this study will be provided a consent form describing this study and providing sufficient information for subjects to make an informed decision about their participation in this study. This consent form will be submitted with the protocol for review and approval by the IRB for the study. The formal consent of a subject, using the IRB-approved consent form, must be obtained before that subject is submitted to any study procedure. This consent form must be signed by the subject or legally acceptable surrogate, as outlined in the IRB approved protocol, and the investigator-designated research professional obtaining the consent.

17 STUDY FINANCES

17.1 Conflict of Interest

Any investigator who has a conflict of interest with this study (patent ownership, royalties, or financial gain greater than the minimum allowable by their institution, etc.) must have the conflict reviewed by the Columbia University Conflict of Interest Committee with a Committee-sanctioned conflict management plan that has been reviewed and approved prior to participation in this study. All CUMC investigators will follow the University conflict of interest policy. All other sites will follow their local conflict of interest policies.

17.2 Subject Stipends or Payments

There are no subject payments or stipends.

18 PUBLICATION PLAN

Bristol-Myers Squibb will be provided with a copy of each publication and any form of public disclosure prior to submission to a journal, publisher, meeting or presentation.

20 APPENDICES

20.1 Appendix 1

20.2 Appendix 2: Methods of Contraception

At a minimum, subjects must agree to use one highly effective method of contraception as listed below:

HIGHLY EFFECTIVE METHODS OF CONTRACEPTION

Highly effective methods of contraception have a failure rate of < 1% when used consistently and correctly. WOCBP and female partners of male subjects, who are WOCBP, are expected to use one of the highly effective methods of contraception listed below. Male subjects must inform their female partners who are WOCBP of the contraceptive requirements of the protocol and are expected to adhere to using contraception with their partner. Contraception methods are as follows:

- 1) Progestogen only hormonal contraception associated with inhibition of ovulation.
- 2) Hormonal methods of contraception including oral contraceptive pills containing combined estrogen + progesterone, vaginal ring, injectables, implants and intrauterine devices (IUDs) such as Mirena®
- 3) Nonhormonal IUDs, such as ParaGard®
- 4) Bilateral tubal occlusion
- 5) Vasectomised partner with documented azoospermia 90 days after procedure
 - Vasectomised partner is a highly effective birth control method provided that partner is the sole sexual partner of the WOCBP trial participant and that the vasectomized partner has received medical assessment of the surgical success.
- 6) Intrauterine hormone-releasing system (IUS).
- 7) Complete abstinence
 - Complete abstinence is defined as the complete avoidance of heterosexual intercourse (refer to Glossary of Terms)
 - Complete abstinence is an acceptable form of contraception for all study drugs and must be used throughout the duration of the study treatment (plus approximately 5 half-lives of the investigational drug plus 30 days).
 - It is not necessary to use any other method of contraception when complete abstinence is elected.
 - Subjects who choose complete abstinence must continue to have pregnancy tests, as specified in Section 12.
 - Acceptable alternate methods of highly effective contraception must be discussed in the event that the subject chooses to forego complete abstinence.
 - The reliability of sexual abstinence needs to be evaluated in relation to the duration of the clinical trial and the preferred and usual lifestyle of the subject.

UNACCEPTABLE METHODS OF CONTRACEPTION

- 1) Periodic abstinence (calendar, symptothermal, post-ovulation methods)
- 2) Withdrawal (coitus interruptus)

- 3) Spermicide only
- 4) Lactation amenorrhea method (LAM)

20.3 Appendix 3. Guidelines for Affiliate Institutions in Multicenter Studies with Columbia University as the Leading Site

1. Multi-site Communication:

The CPDM Office at CUMC provides administration, data management, and organizational support for the affiliate sites in the conduct of a multicenter clinical trial. The CPDM Multicenter Office will coordinate, at minimum, regularly scheduled conference calls with affiliate sites.

The following issues will be discussed, as appropriate:

- Enrollment information
- Adverse events (e.g., new adverse events and updates on unresolved adverse events and new safety information)
- Protocol violations
- Other issues affecting the conduct of the study

2. New Protocol Distribution, IRB Submission, Modifications, and Annual Renewals

- Protocol specific documents are distributed to affiliate sites once CUMC IRB approval has been obtained.
- The affiliate site must submit a draft of site specific revisions to protocol and/or consent form documents for review and approval by the sponsor-investigator prior to submission to the local IRB. Draft documents should be sent to the study specific email address. The site will be provided confirmation that they are approved to submit to their local IRB.
- Protocol amendments must be approved by the affiliate site's local IRB within 90 days of distribution to the site by the sponsor-investigator.

3. Regulatory Documents:

Prior to Site Initiation:

Sponsor-Investigator will ensure that proper requests are made of sites and that the following documentation is collected, prior to the initiation of an affiliate site.

- CV of PI, Co-I's and other research staff listed on FDA 1572 (signed and dated copy within 2 years)
- Medical Licenses of PI and Co-I's (current copy)
- Human subjects training certificates for PI and Co-I's
- CLIA/Laboratory Certifications for Local Laboratories listed on FDA 1572
- Local Laboratory Director's CV and License
- Local Laboratory Reference Ranges
- IRB roster or statement of compliance
- FDA Form 1572, if applicable (wet ink originals required)
- Financial Disclosure forms for all members listed on FDA 1572 (wet ink originals required)

Ongoing Regulatory Documentation: Sponsor-Investigator will ensure that proper requests are made of sites and that the following documentation is collected throughout the course of the study.

- IRB approval letters for all protocol modifications and all renewals
- IRB-approved consent forms
- Current IRB roster, if statement of compliance is not provided as part of site initiation
- FDA Form 1572, if applicable as updates are required
- Updated investigator and site information where relevant (e.g., CV, medical licensure and Financial Disclosure for new sub-investigator, local laboratory information)

Regulatory documents may be sent to the CPDM Multicenter Core at [contact] or to the following address if wet ink originals are required:

Clinical Protocol & Data Management Office
[name]
Herbert Irving Pavilion
[name]
[name]

4. Site activation

Columbia University will schedule a site initiation visit (via teleconference) once IRB approval has been submitted from the affiliate site.

5. Central Registration Procedures- Affiliate Institution Research Participant Registration Process:

All Affiliate Institutions **must** register subjects with the coordinating center (CUMC) **prior** to any administration of study drug/intervention/local institution registration. Please send all Affiliate Site Registrations to [contact]. Please see instructions below:

1. Within 48 hours of obtaining consent (excluding holidays and weekends), the Affiliate Institution CRN and/or CRC is required to submit the following documents to the coordinating center's designee (CUMC Multicenter Trials Core at [contact]). The coordinating center's designee will review the documents for accurateness, and subsequently submit the documents to the CPDM Central Registration Office via email with a request to register the patient "pending eligibility." The title of the email should read, "AAAR6354 Pending Subject Registration Request (PHI)". The following documents should be submitted with the pending registration request, as applicable:

Columbia University Medical Center
Herbert Irving Comprehensive Cancer Center
Version Date: January 30, 2024

- a. Redacted Completed/signed IRB approved/stamped Informed Consent Forms, including additional study ICFs (e.g., tissue, DNA, etc.), as applicable
 - b. Redacted Signed HIPAA (or institutional equivalent)
 - c. MCT CPDM Velos Note to File form
2. The Affiliate Institution's investigator/research nurse/data manager/coordinator must contact the coordinating center's designee CUMC Multicenter Trials Corevia telephone or email to communicate the following:
 - Notify of pending registration request
 - Confirm method of registration request submission (email or fax)
 - Communicate expected time-line of registration request submission (e.g., same day, next day, within the hour, etc.)
3. To complete registration, the Affiliate Institution's investigator/research nurse/data manager/coordinator should then submit the following documents to the CUMC Multicenter Trials Core at [contact]:
 - A signed Affiliate Site Eligibility Checklist (signed by the investigator)
 - Copies of redacted source documentation necessary for each item to be verified on the CUMC specific Eligibility Checklist, including but not limited to:
 - Copy of required laboratory test and procedure reports (e.g., hematology, serum chemistry, pregnancy test when applicable, MRI reports, CT/bone scans, etc.)
 - Copy of pathology and surgical reports
 - Copy of clinic note(s) capturing the consent process information, along with providing source documentation of any other items needed for screening/eligibility that are not captured in other source document forms. (e.g., positive investigator statements of unique eligibility items not captured via other direct source documentation, concomitant medication lists, etc.)
 - Protocol deviation/waiver approvals (if applicable)
 - **Please note:** subject line of email or fax should include the following: "AAAR6354 Complete Subject Registration Request (PHI)".
4. Upon receipt of the above mentioned documents, the designated study specific Clinical Research Coordinator will review all documents and verify patient eligibility. If any questions arise during the review process, queries in the form of emails will be addressed to the applicable affiliate site study team personnel for clarification prior to enrollment. Upon verification, the CUMC Multicenter Core will then forward all documents to the CPDM Central Registration Office for central registration (as described above). The CPDM Central Registration Registrar will review all applicable documents and communicate to the CUMC study specific designee in order to clarify any items. The CUMC study specific designee will communicate with the applicable site study team personnel for additional clarifications necessary prior to enrollment.

5. Upon receipt of the subject registration notification email, the CUMC Multicenter Core will forward the notification email (which will include the study specific patient ID) to the affiliate site's Principal Investigator, Consenting Professional, and applicable research personnel. This notification should be filed in the patient research binder accordingly. Protocol therapy **may not** be initiated prior to receipt of this notification from the coordinating center.
6. All screenfail/ineligible subjects, as well as subject's who withdraw consent prior to enrollment/initiation of protocol therapy must be submitted to the Central Registration Office in a manner analogous to the procedures noted above. Applicable source documentation will be required within the corresponding submissions.

6. Protocol Deviation/Subject Waiver request for Affiliate Sites:

The Affiliate site MUST submit a prospective deviation request to the CUMC lead PI for review and submission to the HICCC DSMC and CUMC IRB. Approvals must be obtained from all entities prior to implementation at the Affiliate site. If a prospective protocol deviation request is submitted for review (from an Affiliate site), the PI/site memo(s), HICCC DSMC approval(s) and correspondence and CUMC IRB approval letter(s)/equivalent should be forwarded to the Affiliate site for documentation. The Affiliate site is also required to obtain prospective local IRB approval as per institutional policies/procedures prior to implementing the proposed deviation. All documents and determinations must be clearly documented in the study subject's medical record, research chart and regulatory binder, as described.

Please note that the HICCC DSMC and PRMC do not approve eligibility deviations. If eligibility deviations are submitted, they will not be approved.

7. *Guidelines for Affiliate Site Monitoring*

On-Site MCT Monitoring:

1. Initial, recurrent, and close-out on-site monitoring visits will also be conducted at Affiliate sites, as appropriate/feasible. Other sites will have monitoring performed remotely (see below for further details).
 - a. The study Monitoring Visit Log will be completed and signed by the monitor and the PI/CRNP/CRN and/or CRC and will be filed in the regulatory binder.
2. The Compliance Coordinator will communicate with the Affiliate site coordinator/Site Principle Investigator to schedule the monitoring visit and arrange for access to study materials and documentation.
3. The Compliance Coordinator will monitor IIT trials within 1 month after the first subject is enrolled at the Affiliate site and throughout the life of the study to ensure that the study is being conducted in accordance with the protocol, GCP, applicable federal and local regulations, and per all applicable SOPs. The Compliance Coordinator is responsible to notify the participating site PI and CRNP/CRN/CRC of upcoming monitor visits and convey what information and documentation will be required for the visit(s). The Compliance Coordinator is responsible for verifying that informed consent is properly

obtained, eligibility is met (via the central registration process), and all study procedures are conducted according to the study protocol. The Compliance Coordinator will also verify that the data reported in the CRF's accurately reflect source documents, that all toxicities have been reported to date, and that all SAE's/UPs/deviations/violations have been reported according to Coordinating Center, local IRB and HICCC DSMC requirements. The Compliance Coordinator will issue queries and ensure resolution in a timely and efficient manner. The Compliance Coordinator will also monitor for applicable regulatory compliance and research pharmacy compliance (if applicable) and communicate any deficiencies as appropriate.

4. An SIV (or) teleconference will be scheduled and conducted prior to study drug being made available (if applicable) and before any subjects are enrolled on a study at the Affiliate site.

MCT Remote Monitoring:

- When necessary (due to logistical constraints), Affiliate sites will be monitored remotely by a designated Compliance Coordinator. Sites will be informed of this remote monitoring process on a site by site basis.
- Affiliate sites will be monitored by the Compliance Coordinator on both a regulatory level, as well as a clinical data/source documentation review level.
- Redacted source documents (applicable to supporting the protocol specific CRF data requirements) will be sent to the designated Compliance Coordinator via fax or secure email for all subjects enrolled at Affiliate sites. Timelines for submission procedures will be defined on a case by case basis.
- The Compliance Coordinator will review all submitted redacted source documents against the data entered on the protocol specific CRFs. The Compliance Coordinator will issue queries when/if necessary.
- The Affiliate site research staff will respond to queries within 30 days. If queries remain outstanding, the Compliance Coordinator will send a delinquent query reminder for the outstanding items.
- The remote monitoring procedures will include review of applicable redacted source documentation and supporting applicable documents to determine compliance regarding:
 - a. Informed consent procedures
 - b. Eligibility criteria
 - c. Protocol specific treatment compliance
 - d. Protocol specific toxicity/outcome documentation/compliance
 - e. Protocol specific schedule of events (e.g., baseline visits, pre-treatment, on study, follow-up)
 - f. Participating site IRB documents (e.g., IRB amendment approvals, annual renewals, SAE/UP submissions, violation/deviation submissions, INDSR submissions, etc.).
 - g. Required specimen submissions (e.g., tissue specimens, research blood specimens, etc.)
 - h. Pharmacy accountability records

- i. Adherence to the CRF submission timeframes to CUMC (within the protocol specified timeframes)
- Affiliate site remote monitoring reports will be sent to the lead PI, HICCC DSMC, and Affiliate sites after each remote monitoring review. Reports will include information regarding data submission timeliness/accuracy, protocol adherence items, query resolution status, regulatory status, and overall Affiliate site performance. These reports will be generated by the Compliance Coordinator and reviewed with the Compliance Core Manager prior to dissemination.

8. Adverse event reporting

Sponsor reporting: Notifying participating investigators at affiliate sites of adverse events

It is the responsibility of the study sponsor to notify all affiliate sites, in a written IND safety report, of any adverse event associated with the use of the drug that is both serious and unexpected, as well as any finding from tests in laboratory animals that suggest a significant risk for human subjects. Additionally, sponsors are also required to identify in IND safety reports all previous reports concerning similar adverse events and to analyze the significance of the current event in light of the previous reports.

Serious Adverse Event Reporting

Each participating investigator is required to abide by the reporting requirements set by Columbia University Medical Center. The study must be conducted in compliance with FDA regulations, local safety reporting requirements, and reporting requirements of the principal investigator.

Participating investigators must report each serious adverse event to the Columbia University Medical Center Overall Principal Investigator within 24 hours of learning of the occurrence using the SAE Report Form. In the event that the participating investigator does not become aware of the serious adverse event **immediately** (e.g., participant sought treatment elsewhere), the participating investigator is to report the event within 24 hours after learning of it and document the time of his or her first awareness of the adverse event. Report serious adverse events by telephone, email or facsimile to:

[name]
[name]
[name]
[contact]
[contact]
Email: [contact]

The participating investigator must provide follow-up information on the serious adverse event until event resolution. Follow-up information should describe whether the event has resolved or continues, if and how the event was treated, and whether the participant will continue or

discontinue study participation.

Follow-up information is sent to the same person to whom the original SAE Report Form was sent, using a new SAE Report Form stating that this is a follow-up to the previously reported SAE and giving the date of the original report. Each re-occurrence, complication, or progression of the original event should be reported as a follow-up to that event regardless of when it occurs. The follow-up information should describe whether the event has resolved or continues, if and how it was treated, and whether the subject **continued** or withdrew from study participation or if study drug was interrupted or discontinued.

If the SAE is not previously documented in the Investigator's Brochure for the study drug (new occurrence) and is thought to be related to the investigational agent, the sponsor-investigator may urgently require further information from the investigator for reporting to Health Authorities.

Non-Serious Adverse Event Reporting

Non-serious adverse events will be reported to the Columbia University Medical Center Overall Principal Investigator on the toxicity Case Report Forms in Velos eResearch.

Reporting to the Institutional Review Board (IRB) and the Data and Safety Monitoring Committee:

All Unanticipated Problems (UPs) will be reported to the CUMC IRB. SAEs not constituting UPs will be reported to the HICCC DSMC.

